#### 9.11. Digits of numerical values to be displayed

Digits of numerical values should be as shown below.

Type of numerical value	Digits to be displayed
Mean value, standard deviation, median value, first quartile, third quartile, 95% confidence interval	Figures should be rounded to the significant digits of the data +2 digit and displayed as the significant digit of the data +1 digit
Minimum and maximum values	Figures should be displayed with the same number of digits as the displayed digits of the data

Type of numerical value	Digits to be displayed
Number of patients	Figures should be displayed as integer values
Percentage	Figures should be rounded to the first decimal place and displayed to one place of decimal However, it should be specified in the analysis result output sheet when figures in Appended Form 2 and the incidence rates of adverse events, etc. are rounded to the second decimal place and displayed to two places of decimal.
p value	Figures should be rounded down to the fourth decimal place and displayed to four places of decimal However, figures smaller than 0.0001 should be displayed as <0.0001 without exception

#### 9.12. Rules for displaying numerical values

Case	Display rule
When a figure cannot be calculated	Hyphen “-”
When displaying blank	If any analysis result should be displayed as blank, it should be specified in a footnote what blank indicates

#### 9.13. Test methods

In this analysis plan, a paired t-test should be conducted for the amount of change from before the start of administration. For the incidence rates and remission rates (DAS28) of adverse reactions for each background factor, Fisher's exact test or Mann-Whitney U test should be conducted. Tests should not include an unknown/unspecified category.

#### 9.14. Level of significance

In principle, the significance level of statistical analyses used in this survey is two-sided 5%.  $p < 0.05$  ( $< 5\%$ ) should be considered significant.

#### 9.15. Diagram-specific rules

##### 1) Appended Form 2, Appended Form 10, Appended Form 3

- A) Forms should be created in accordance with the latest version of “Guidance for Application for Reexamination, Japan Pharmaceutical Information Center”.
- B) Separation of the reporting period for Appended Form 2 and Appended Form 10 is as follows.

In principle, this should be the survey unit period defined in the analysis implementation schedule. However, when the size of the printed page does not fit into A4, the period should be determined upon consultation with the entrustor.

## 10. Data derivation and calculation methods

### 10.1. General

Name of data	Derivation and calculation methods
Age	Use the age shown in the CRF.
Number of investigating facilities	Aggregate the data for each facility code (DCF code).
Number of patients surveyed	Number of patients included in the safety analysis set.
Start date of Humira treatment	Of the start dates of treatment provided in “2. Status of Humira treatment”, the earliest date will be the start date of Humira treatment in each patient. (See “External file for provision of analysis”)
End date of Humira treatment	The latest date sorted by the end dates of treatment provided in “2. Status of Humira treatment” will be the end date of Humira treatment in each patient. (See “External file for provision of analysis”) In the case of ongoing patients, the date on which the final dosing was completed, which is provided in the CRF, will be the end date of Humira treatment. However, in patients whose end date of Humira treatment is “ongoing” or where the end date of Humira treatment calculated as above exceeds the start date of Humira treatment + 168 days, the end date of Humira treatment should be the start date of Humira treatment + 168 days.
Days to the date on which the last dosing of Humira was completed	End date of Humira treatment - Start date of Humira treatment + 1
Treatment status (total number of doses, total dose)	
 
• Total number of doses
 
 
(1) Data on “start date of treatment” and “number of doses” in “2. Status of Humira treatment” should be sorted in the order they are written.
 
(2) Dosing intervals should be calculated for each data on treatment status.
 
The intervals should be 14 days if “biweekly” is checked. If not, the intervals should be obtained from “External file for provision of analysis”.
 
(3) The number of doses should be calculated for each data on treatment status.
 
Number of doses = (end date of treatment [after complementation] - start date of treatment [after complementation])/dosing intervals (days)
 
*The end date of treatment in the last record should be the end date of Humira treatment.
 
(4) If the result of (3) is “>0” (greater than 0) and “<1” (smaller than

Name of data	Derivation and calculation methods
	
1), it should be 1.
 
If “>=1” (1 or greater), the number should be rounded down to the nearest integer.
 
(5) The total number of doses should be the sum of (4) for each patient.
 
 
• Total dose
 
 
(1) If the dose of Humira is “other”, it should be obtained from “External file for provision of analysis”.
 
(2) Doses should be calculated for each data on treatment status.
 
Dose = number of doses x dose
 
(3) The total dose should be the sum of (2) for each patient.
 
 
• Mean dose
 
 
Mean dose = total dose / total number of doses

Discontinued patients	When the end date of Humira treatment is less than 24 weeks (168 days) after the start date of Humira treatment, the patient should be handled as a discontinued patient.
Reason for discontinuation	In the case of discontinued patients, data should be derived from “Reason for discontinuation” under “3. Discontinuation of treatment” of the CRF or “External file for provision of analysis”. If any data have not been provided, it should be handled as “unknown/unspecified”. “Onset of an adverse event” should apply only when “Onset of an adverse event” is selected and an adverse event during the safety analysis period has occurred.
Date of discontinuation of treatment	In the case of discontinued patients, the end date of Humira treatment should be the date of discontinuation. Where the start date of Humira treatment + 168 days > the end date of Humira treatment, the end date of Humira treatment should be the date of discontinuation.
Patients switched to other biological products	Patients falling under discontinued patients, for whom “Switching to another drug” is selected for “Treatment status after discontinuation” under “3. Discontinuation of treatment” of the CRF and whose “Drug name” falls under codes of biological products listed in “Drug code list 20171012.xlsx”.
Reason for switching	In the case of patients switched to other biological products, data should be derived from “Reason for discontinuation” under “3. Discontinuation of treatment” of the CRF or “External file for provision of analysis”. If any data have not been provided, it should be handled as “unknown/unspecified”. “Onset of an adverse event” should apply only when “Onset of an adverse event” is selected and an adverse event during the safety analysis period has occurred.

Name of data	Derivation and calculation methods
Status of complications	“With complication” should be selected when the patient has any of the diseases listed under “Complications” in the CRF, “unknown/unspecified” should be selected when “Status of complications” in the CRF is not specified or indeterminable, and “without complication” should be selected otherwise.
Past medical history	“With past medical history” should be selected when the patient has any of the diseases listed under “Past medical history” in the CRF, “unknown” should be selected when “Past medical history” in the CRF is “unknown” or unspecified or indeterminable, and “without past medical history” should be selected otherwise.
Complication: Liver disorder	“With liver disorder” should be selected when the patient has data for “hepatitis”, “hepatitis virus carrier”, “hepatic cirrhosis”, “hepatic steatosis” or “other” in “Complications/Liver disorder” in the CRF, “unknown/unspecified” should be selected when “Status of complications” is not specified or indeterminable, and “without liver disorder” should be selected otherwise.
Complication: Renal disorder	“With renal disorder” should be selected when the patient has data for “nephritis”, “renal failure”, “nephrotic syndrome” or “other” in “Complications/Renal disorder” in the CRF, “unknown/unspecified” should be selected when “Status of complications” is not specified or indeterminable, and “without renal disorder” should be selected otherwise.
Complication: Cardiovascular disorder	“With cardiovascular disorder” should be selected when the patient has data for “arrhythmia”, “Kawasaki's disease”, “hypertension” or “other” in “Complications/Cardiovascular disorder” in the CRF, “unknown/unspecified” should be selected when “Status of complications” is not specified or indeterminable, and “without cardiovascular disorder” should be selected otherwise.
Complication: Blood disorder	“With blood disorder” should be selected when the patient has data for “aplastic anaemia”, “anaemia”, “pancytopenia” or “other” in “Complications/Blood disorder” in the CRF, “unknown/unspecified” should be selected when “Status of complications” is not specified or indeterminable, and “without blood disorder” should be selected otherwise.

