Data	Layer separation
disorder	
Complication: Cardiovascular disorder	No, yes, unknown/unspecified
Complication: Blood disorder	No, yes, unknown/unspecified
Complication: Respiratory disorder	No, yes, unknown/unspecified
Complication: Other	No, yes, unknown/unspecified
History of allergy	No, yes, unknown/unspecified
Breakdown of history of allergy	Drug, food, other
Previous medications	No, yes, unknown/unspecified
Breakdown of previous medications	Methotrexate, corticosteroid, NSAIDs, other DMARDs
History of treatment with previous medications (biological products)	No, yes, unknown/unspecified
Breakdown of history of treatment with previous medications (biological products)	Tocilizumab, etanercept, other
Concomitant drugs	No, yes, unknown/unspecified
Breakdown of combination drugs	Methotrexate, corticosteroid, NSAIDs, other DMARDs, other drugs
Tuberculin skin test	Tested, not tested, unknown/unspecified
Quantiferon test (including T-SPOT)	Tested, not tested, unknown/unspecified
Chest x-ray	Tested, not tested, unknown/unspecified
Chest CT	Tested, not tested, unknown/unspecified
Immunology test (tuberculin skin test or Quantiferon test or T-SPOT)	No, yes, unknown/unspecified
Image testing (chest x-ray or chest CT)	No, yes, unknown/unspecified
Prophylactic administration (status of prophylactic administration by	No, yes, unknown/unspecified

Data	Layer separation
implementation status of tuberculosis tests)	
HBs antigen test	Implemented (negative, positive, unknown/unspecified, subtotal), not implemented, unknown/unspecified
HBs antibody test	Implemented (negative, positive, unknown/unspecified, subtotal), not implemented, unknown/unspecified
HBc antibody test	Implemented (negative, positive, unknown/unspecified, subtotal), not implemented, unknown/unspecified
Status of Humira treatment (dosage and administration)	20 mg/2 weeks, 40 mg/2 weeks, 20 mg/2 weeks → 40 mg/2 weeks, other
Number of doses	≥1 to <2 doses, ≥2 to <6 doses, ≥6 to <12 doses, ≥12 doses
Days to the date of the last dosing	1 to 28 days, 29 to 84 days, 85 to 168 days, ongoing at day 169
Dose at the start of Humira treatment	20 mg, 40 mg, 80 mg, other, unknown/undescribed
Dosage and administration category	Dose increase group (20 mg → 40 mg), maintained dose group, other, unknown/unspecified
Self-administration	No, yes, unknown/unspecified
Error caused by self-administration	No, yes, unknown/unspecified

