  - Status: Output “status of complications” defined in “10.1 General”.
  - Number provided: This should be the number of PT codes for complications coded with MedDRA/J. The same PT codes in a single patient should be considered as one case. Where there is no complication, this should be “0”.
  - Name: This should be PT terms for complications coded with MedDRA/J. Detailed categories of complications, disease names of complications, and sequential numbers of complications should be arranged in the sequential order for each patient. Leave this blank when the number of cases provided is “0”. Output data should be in the order of MedDRA/J PT code, sequential number, and description in the CRF.
- (12) Route of administration: Output “SC”.
- (13) Maximum dose (per dose): This should be the maximum amount per dose. From doses described in the CRF, the maximum dose should be output for each patient.
- (14) Mean dose (per dose): This should be the average amount per dose. From “treatment status (total number of doses, total dose)” defined in “10.1 General”, values of “total dose/total

number of doses” should be output.

- (15) Unit: Output “MG”.
- (16) Number of daily doses (maximum): Where there is no patient receiving two or more doses per day, “1” should be output.
- (17) Duration of use: From “treatment status (total number of doses, total dose)” defined in “10.1 General”, a value of “total number of doses” should be output.
- (18) Concomitant drugs (drug code, representative drug name, number provided):
  - Drug code, representative drug name: List these in the order of “concomitant drugs for juvenile idiopathic arthritis”, “other concomitant drugs” with sequential numbers, and the concomitant drug listed on the top should be analyzed. Where there is no concomitant drug, the drug code should be blank and the representative drug name should be “none”.
  - Number provided: Count the drug codes rearranged above. Where there is more than one same code for a single patient, they should be counted as one. Where there is no concomitant drug, this should be “0”.
- (19) Degree of effect: Output DAS28-4/ESR (remission, non-remission) at the final assessment. Output “unspecified” if “clinical course” after the start of treatment is unspecified in the CRF, and “unknown” if indeterminable.

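### The SAP 10.1 dose count has no branch for a result of zero and is one short for most early stops unless the end date is the next due date; Table 2.16.2 includes serious events that fit none of its phases

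*SAP*

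**What the plan says.** **Dose count (SAP 10.1, treatment status).** Step (3) gives, for each treatment record, "Number of doses = (end date of treatment [after complementation] - start date of treatment [after complementation])/dosing intervals (days"). The interval is 14 days when biweekly dosing is ticked. A note adds: "The end date of treatment in the last record should be the end date of Humira treatment". Step (4) raises a result above 0 and below 1 to 1; its only other branch reads "1 or greater), the number should be rounded down to the nearest integer". Step (5) sums the records. Mean dose is total dose divided by total number of doses.

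**End date (SAP 10.1).** For patients marked as ongoing, or whose end date passes the limit, "the end date of Humira treatment should be the start date of Humira treatment + 168 days". The row "Days to the date on which the last dosing of Humira was completed" is end minus start plus 1.

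**Where the count goes.** Table 1.9 uses the Section 11 classes "≥1 to <2 doses, ≥2 to <6 doses, ≥6 to <12 doses, ≥12 doses", with none for zero or unknown. In Table 4.4 (Appended Form 3), item (14) prints the mean dose, and for duration of use, item (17), "a value of “total number of doses” should be output". SAP 9.12 prints a hyphen for the case "When a figure cannot be calculated".

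**Phases (SAP 10.2, Tables 2.16.1-2.16.2).** The during phase runs from after the start date to the end or discontinuation date. The after phase runs from there to start + 196 days. Table 2.16.1 is limited to the safety analysis period. Table 2.16.2 takes serious events inside and outside it. SAP Section 2 defines outside as before the start date or after start + 196.

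**The concern.** Elapsed time divided by the interval counts intervals, not injections. The first injection falls on the start date, so the two agree only when the end date is the day the next injection falls due. Step (4) corrects for this below one interval and nowhere else, and it leaves a result of exactly zero untouched. The shortest exposures are therefore the ones with no dose class. The outputs go into the reexamination material.

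The phase tables raise a related problem. The end date is set to start + 168 for patients who continue, so a later event can be called post-treatment while Humira is still being given. Table 2.16.2 also includes events that its two phases do not cover.

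**Working it through.** The plan states no dose count to reproduce, so the check applies its rule to a biweekly schedule. Inputs from SAP 10.1: interval 14 days, cap at start + 168, steps (3) to (5). Days below are offsets from the start date. Assumption: injections are given on schedule, on offsets 0, 14, 28 and so on.

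**Single record, the plan's rule**

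- Capped full course: 168/14 = 12. Injections on offsets 0 to 154 number 154/14 + 1 = 12. Right.
- End = start: 0/14 = 0, with no branch. SAP Section 8 excludes undosed patients from the safety set, so the true count is at least 1. Mean dose is 0/0, yet days to last dosing is 0 + 1 = 1.
- Rounding: 13/14 = 0.93 becomes 1; 27/14 = 1.93 becomes 1; 167/14 = 11.93 becomes 11.

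**Case A: the end date is the last injection.** For m injections the end offset is 14(m - 1), so the rule returns m - 1. Before the cap m runs from 1 to 12, and all 12 stop days are one short. The Table 1.9 class changes at these four:

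| Injections | Rule gives | True class | Class from the rule |
|---|---|---|---|
| 1 | 0 | ≥1 to <2 | none |
| 2 | 1 | ≥2 to <6 | ≥1 to <2 |
| 6 | 5 | ≥6 to <12 | ≥2 to <6 |
| 12 | 11 | ≥12 | ≥6 to <12 |

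**Case B: the end date can fall between injections and is not itself an injection.** The true count at offset e is ceil(e/14), minimum 1. Over offsets 0 to 167:

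- Zero: offset 0, 1 day.
- Right: offsets 1-13 (13 days) and the multiples 14 to 154 (11 days), 24 in all. The multiples are the next-due-date case.
- One short: 168 - 1 - 24 = 143 days.
- Wrong class or none: offset 0, and offsets 15-27, 71-83 and 155-167, so 1 + 3 × 13 = 40 days.

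**Dose change, illustration.** Record 1 is 20 mg with injections on 0 and 14; record 2 is 40 mg from 28, ongoing. If record 1 ends on its last injection, the rule gives 14/14 + 140/14 = 1 + 10 = 11 doses, 20 + 400 = 420 mg, mean 38.2 mg. The injections given are 2 + 10 = 12, 440 mg, mean 36.7 mg. If record 1 ends on offset 28, the rule gives 2 + 10 = 12, which is right.

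**Records after the cap.** Only the last record takes the capped end date. If a last record starts on offset 168, the result is (168 - 168)/14 = 0. If it starts on 182, the result is (168 - 182)/14 = -1. Neither has a branch.

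**Phases.** With the end date set to start + 168, the after phase for a patient who continues is start + 169 to start + 196, or 196 - 169 + 1 = 28 days. The 10.2 onset row takes the start date as Day 1, so its last class, from Day 169, begins at start + 168. That is one day earlier.

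As an example, take eight serious events with different preferred terms on offsets -5, 0, 30, 168, 180, 196, 197 and 400, with treatment ending on 168. During takes 2 (30, 168) and after takes 2 (180, 196). Four have no phase: -5, 197 and 400 lie outside the safety period, and 0 drops out if 'after the start date' is read literally.

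**The case against.** **The CRF may settle the dose count.** Dates are used after complementation and partly come from an external file. If every end date is the next due date, whole intervals are counted correctly, and the capped single-record course is right in any case. This stands as a limit on size. It does not supply the missing branch: SAP 9.1 says completion methods are given from Chapter 10 onward, and none there covers a zero or negative interval. The SAP also describes the end date as the completion of the last dosing, which points towards Case A without proving it.

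**The hyphen rule covers 0/0.** It does for mean dose. It gives the patient no Table 1.9 class, while SAP 9.10 wants breakdown percentages to total 100%.

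**Records after the cap may not exist.** This is fair, since observation lasts 24 weeks. A reader might carry the negative count through to a mean dose. The SAP leaves that result undefined, so no mean dose should be quoted for it.

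**Ongoing patients may not be split by phase.** In Tables 2.16.1-2.16.2 the during/after/overall parenthesis follows the discontinued group and may belong to it alone. On that reading the 28-day window does not affect the ongoing group. The text allows either reading.

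**The phases need not add up.** A reader might infer that during plus after should equal overall in Table 2.16.2. The documents do not support that: a preferred term seen in both phases is counted once by a stated rule. The valid point is narrower, namely that some included events have no phase. They are not lost, because Table 4.2 flags events outside the survey period.

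**Conclusion.** The concern holds as a minor one. The dose-count rule is incomplete at zero and inconsistent in its rounding. It is right for a single record capped at start + 168 and where the end date is the next due date. On an on-schedule biweekly course it is one short on 12 of 12 stop days in Case A and on 143 of 168 in Case B, where one more day gives 0 and 40 get a wrong class or none. These are counts of possible stop days, not shares of patients. The documents do not show how many patients are affected, so the tables cannot be called wrong for any known number.

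The labelling of events from start + 169 to start + 196 is a problem only if the split covers patients ongoing at Week 24 or the entire population. The scope mismatch in Table 2.16.2 is real on the text alone.

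The effect is confined to descriptive exposure and phase tables. Adverse-reaction incidence and the significance tests do not use these quantities.

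**What to change.** **(a) Dose count.** Cap every record's end date at start + 168, and give records starting on or after that day a count of 0. Otherwise:

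- where the end date is an injection date, use floor((end - start)/interval) + 1;
- where it is not (the next record's start, the cap including an end date equal to it, or a date between injections), use ceil((end - start)/interval), minimum 1.

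In Case A this returns (m - 1) + 1 = m. In Case B it is the true count at every offset. A capped full course stays at 12, and the dose-change example gives 2 + 10 = 12. Confirm the end-date convention from the CRF, by record if it is not uniform.

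**(b) Phase label.** State which groups the during/after columns of Tables 2.16.1-2.16.2 cover. For patients not discontinued by Week 24, label the later window by its dates (start + 169 to start + 196), unless a recorded stop date shows that treatment had ended. In the 10.2 onset row use Section 11's after-Week-24 label, and reconcile its boundary (start + 168) with that of Table 2.16 (start + 169).

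**(c) Table 2.16.2.** Add phases for events before the start date and after start + 196. Word the during phase as on or after the start date. Footnote that a preferred term occurring in more than one phase counts once in the overall column.

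**Cost.** SAP wording, the CRF check, and reruns of Table 1.9, Appended Form 3 (Table 4.4) and Tables 2.16.1-2.16.2. Tables 2.14-2.15 already use the Section 11 label and need a rerun only if the onset boundary is the one moved. No new data are needed.

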Administration by a doctor	In “2. Status of Humira treatment” in the registration form, administration is “administration by a doctor” at all timings.
Dosage and administration category: Dose increase group (20 mg → 40 mg)	In “2. Status of Humira treatment” in the registration form, “dose” was increased from 20 mg to 40 mg.
Dosage and administration category: Maintained dose group	In “2. Status of Humira treatment” in the registration form, “dose” was never increased or reduced.
Dosage and administration category: Other	In “2. Status of Humira treatment” in the registration form, “dose” was reduced to below 20 mg, “dose” was increased from 40 mg to 80 mg, “dose” was increased and then reduced, or “number of doses” is other than biweekly.
Patients deviated from	Patients who received Humira at a dose other than “20 mg/2 weeks”

Name of data	Derivation and calculation methods
recommended dosage and administration of Humira	or “40 mg/2 weeks” are defined as patients deviated from the recommended dosage and administration.
Previous medications	Of the drugs listed under “Status of administration of concomitant drugs” in “5. Previous medications for juvenile idiopathic arthritis” in the CRF and confirmed to have been administered between the start date of Humira treatment - 90 days and the start date of Humira treatment - 1 day, drugs falling under “MTX”, “DMARDs”, “steroid (oral + injection)” or “NSAIDs (oral + injection)” in “Drug code list_20171012.xlsx” are defined as previous medications.
Status of previous medications	“With previous medications” should be selected when the patient was previously treated with medications, “unknown/unspecified” should be selected when “Status of previous medications for juvenile idiopathic arthritis” is not specified or indeterminable, and “without previous medications” should be selected otherwise.
Previous medication: Methotrexate	“With previous medication: methotrexate” should be selected when the conditions for “previous medications” are met and the previous medication falls under “MTX” in “Drug code list_20171012.xlsx”, “unknown/unspecified” should be selected when the status of previous medications is “unknown/unspecified”, and “without previous medication: methotrexate” should be selected otherwise.
Previous medication: Corticosteroid	“With previous medication: corticosteroid” should be selected when the conditions for “previous medications” are met and the previous medication falls under “steroid (oral + injection)” in “Drug code list_20171012.xlsx”, “unknown/unspecified” should be selected when the status of previous medications is “unknown/unspecified”, and “without previous medication: corticosteroid” should be selected otherwise.
Previous medication: NSAIDs	Drugs that meet the conditions for “previous medications” and fall under “NSAIDs (oral + injection)” in “Drug code list_20171012.xlsx”.
Previous medication: Other DMARDs	“With previous medication: other DMARDs” should be selected when the drug meets the conditions for “previous medications” and does not fall under “MTX” and falls under “DMARDs” in “Drug code list_20171012.xlsx”, “unknown/unspecified” should be selected when the status of previous medications is “unknown/unspecified”, and “without previous medication: other DMARDs” should be selected otherwise.
Previous medication (biological products)	Drugs listed in “4. History of treatment with biological products for juvenile idiopathic arthritis” (which applies to all biological products previously used) in the CRF should be all previous medications (biological products) confirmed to have been administered between the start date of a biological product and the start date of Humira

Name of data	Derivation and calculation methods
	treatment - 1 day. Alternatively, of the drugs listed under “Status of administration of concomitant drugs” in “5. Previous medications for juvenile idiopathic arthritis” in the CRF and confirmed to have been administered between the start date of Humira treatment - 90 days and the start date of Humira treatment - 1 day, drugs falling under “biological products” in “Drug code list_20171012.xlsx” are defined as previous medications (biological products).
History of treatment with previous medications (biological products)	“With a history of treatment with previous medications (biological products)” should be selected when the patient was previously treated with medications (biological products), “unknown/unspecified” should be selected when “History of treatment with biological products” is not specified or indeterminable, and “without a history of treatment with previous medications (biological products)” should be selected otherwise.
Previous medication (biological product): tocilizumab	“With previous medication (biological product): tocilizumab” should be selected when the drug meets the conditions of “previous medications (biological products)” and the higher order 7 digits of the drug code of the previous medication (biological product) are “6399421”, “unknown/unspecified” should be selected when the history of treatment with previous medications (biological products) is “unknown/unspecified”, and “without previous medication (biological product): tocilizumab” should be selected otherwise.
Previous medication (biological product): etanercept	“With previous medication (biological product): etanercept” should be selected when the drug meets the conditions of “previous medications (biological products)” and the higher order 7 digits of the drug code of the previous medication (biological product) are “3999424”, “unknown/unspecified” should be selected when the history of treatment with previous medications (biological products) is “unknown/unspecified”, and “without previous medication (biological product): etanercept” should be selected otherwise.
Previous medication (biological product): other	“With previous medication (biological product): other” should be selected when the drug meets the conditions of “previous medications (biological products)” and the higher order 7 digits of the drug code of the previous medication (biological product) are other than “6399421” and “3999424” and the drug falls under “Biological products” in “Drug code list_20171012.xlsx”, “unknown/unspecified” should be selected when the history of treatment with previous medications (biological products) is “unknown/unspecified”, and “without previous medication (biological product): other” should be selected otherwise.
Concomitant drugs	Concomitant drugs are defined as drugs listed in “5. Previous medications for juvenile idiopathic arthritis”, “6. Status of

Name of data	Derivation and calculation methods
	administration of concomitant drugs (1) [Concomitant drugs for juvenile idiopathic arthritis]”, “6. Status of administration of concomitant drugs (2) [Other concomitant drugs]” in the CRF and confirmed to have been administered between the start date of Humira treatment and the end date of Humira treatment.
Status of concomitant drugs	“With concomitant drugs” should be selected when the patient is treated with concomitant drugs, “unknown/unspecified” should be selected when “Status of previous medications for juvenile idiopathic arthritis/concomitant drugs for juvenile idiopathic arthritis/other concomitant drugs” is not specified or indeterminable, and “without concomitant drugs” should be selected otherwise.
Concomitant drug: methotrexate	“With concomitant drug: methotrexate” should be selected when the conditions for “concomitant drugs” are met and the concomitant drug falls under “MTX” in “Drug code list_20171012.xlsx”, “unknown/unspecified” should be selected when the status of concomitant drugs is “unknown/unspecified”, and “without concomitant drug: methotrexate” should be selected otherwise.
Concomitant drug: corticosteroid	“With concomitant drug: corticosteroid” should be selected when the conditions for “concomitant drugs” are met and the concomitant drug falls under “steroid (oral + injection)” in “Drug code list_20171012.xlsx”, “unknown/unspecified” should be selected when the status of concomitant drugs is “unknown/unspecified”, and “without concomitant drug: corticosteroid” should be selected otherwise.
Concomitant drug: NSAIDs	“With concomitant drug: NSAIDs” should be selected when the conditions for “concomitant drugs” are met and the concomitant drug falls under “NSAIDs (oral + injection)” in “Drug code list_20171012.xlsx”, “unknown/unspecified” should be selected when the status of concomitant drugs is “unknown/unspecified”, and “without concomitant drug: NSAIDs” should be selected otherwise.
Concomitant drug: other DMARDs	“With concomitant drug: other DMARDs” should be selected when the drug meets the conditions for “concomitant drugs” and does not fall under “MTX” and falls under “DMARDs” in “Drug code list_20171012.xlsx”, “unknown/unspecified” should be selected when the status of concomitant drugs is “unknown/unspecified”, and “without concomitant drug: other DMARDs” should be selected otherwise.
Concomitant drug: Other drugs	“With concomitant drug: other drugs” should be selected when the drug meets the conditions for “concomitant drugs” and does not fall under “MTX”, “steroid (oral + injection)” or “DMARDs” in “Drug code list_20171012.xlsx”, “unknown/unspecified” should be selected when the status of concomitant drugs is “unknown/unspecified”, and

Name of data	Derivation and calculation methods
	“without concomitant drug: other drugs” should be selected otherwise.
Tuberculin reaction	Related data should be derived from “Tuberculin skin test” in the registration form.
Quantiferon test (including T-SPOT)	Related data should be derived from “Quantiferon test”, “External file for provision of analysis (a list of T-SPOT)” in the registration form.
Chest x-ray	When the date of chest x-ray between the start date of Humira treatment - 90 days and the start date of Humira treatment is provided in “8. Occurrence of tuberculosis and serious respiratory disorder” in the registration form, the patient is defined as those who underwent chest x-ray.
Chest CT	When the date of chest CT between the start date of Humira treatment - 90 days and the start date of Humira treatment is provided in “8. Occurrence of tuberculosis and serious respiratory disorder” in the registration form, the patient is defined as those who underwent chest CT.
Prophylactic administration (status of prophylactic administration by implementation status of tuberculosis tests)	Related data should be derived from “prophylactic administration or antituberculosis drugs” in the registration form.
Status of combination therapy for juvenile idiopathic arthritis	“With combination therapy for juvenile idiopathic arthritis” should be selected when data is provided for “7. Non-drug combination therapy for juvenile idiopathic arthritis” in the CRF, “unknown/unspecified” should be selected when “Status of combination therapy” is not specified or indeterminable, and “without combination therapy” should be selected otherwise.
Combination therapy for juvenile idiopathic arthritis: rehabilitation	The detail of combination therapy falls under “Contents of implementation/rehabilitation” in the “External file for provision of analysis”.
Combination therapy for juvenile idiopathic arthritis: other	The detail of combination therapy falls under “Contents of implementation/other” in the “External file for provision of analysis”.
Combination therapy for juvenile idiopathic arthritis: unknown/unspecified	The detail of combination therapy falls under “Contents of implementation/unknown, unspecified” in the “External file for provision of analysis”.
Dose of concomitant drug methotrexate per body surface area	In the case of concomitant drug methotrexate, body surface area should be calculated with the use of data before the start of treatment in “9. Clinical course” in the CRF and the dose of methotrexate per

Name of data	Derivation and calculation methods
	
body surface area should be calculated.
 $S = W^{0.425} \times H^{0.725} \times 71.84$ 
S = body surface area (cm^2); W = body weight from the start date of Humira treatment - 28 days to the start date of Humira treatment (kg); H = height from the start date of Humira treatment - 28 days to the start date of Humira treatment (cm)
 
If the dose of methotrexate was changed during the survey period, calculate doses per body surface area for each record and calculate the mean value.

